# 9.8 Additional Analyses of the Effects of the Interventions

In addition to considering effects of the interventions on outcome at 4 and 12 months, contrasts will be constructed to estimate their effects on the change from 4 to 12 months to determine if treatment effects are changing over time. For quantitative outcomes obtained monthly, the basic model will be extended to evaluate patterns of change incorporating each protocol time point. Due to the larger number of time points, the covariance matrix of the residuals will be estimated under a mixed effects model including random effects (e.g., a random intercept and slope) and additional correlation parameters as needed to fit the serial correlation structure of the data [Littell, 1996;Verbeke, 1998].

Concentrations of serum albumin, hematocrit, and hemoglobin as well as body weight may shift shortly after initiation of nocturnal home hemodialysis due to altered extracellular volume, complicating interpretation of longitudinal changes. Thus, we plan to supplement tests of effects of the treatment interventions on changes from baseline to month 4 or month 12 (which may overestimate beneficial effects of the nocturnal hemodialysis intervention due to hemoconcentration) with contrasts evaluating the changes from the 1-month visit, at which time most hemoconcentration effects should have occurred. Contrasts for changes from baseline to the 1-month visit will be used to estimate the size of the change in extracellular water and the associated hemoconcentration effects.

Analyses will also be used to test for interactions between the treatment interventions and prespecified baseline factors to evaluate whether certain subgroups experience increased or reduced benefits of the interventions. The Steering Committee has pre-specified the following factors for evaluation of treatment interactions:

History of heart disease, gender, anthropometric volume (Watson volume < 35 L vs.  $\ge 35$  L), years of dialysis (< 2 years vs.  $\ge 2$  years), presence of residual renal function (defined by > 100 mL urine volume per 24 hours).

Additional analyses will also be performed to determine if the primary and secondary outcomes differ based on the utilization of single needle versus double needle dialysis in patients randomized to the nocturnal arm of the study.

The primary and main secondary analyses will also be repeated after excluding those patients who were randomized prior to the modification of the conventional hemodialysis arm to stipulate home rather than in-center dialysis. [2014 FHN Archive Note: These analyses were not done as agreed by FHN Steering Committee.]

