## 2.2 Overview of Study Design

This will be a randomized, unblinded study of six times per week nocturnal home hemodialysis versus three times per week conventional home hemodialysis. A target of 90 patients will be enrolled into this study with equal allocation in each arm, stratified by Clinical Center and diabetic status. All patients will be assessed for suitability for nocturnal home hemodialysis using a standardized method prior to patients entering the baseline portion of this protocol. The minimum dialysis dose in the conventional home arm will be an equilibrated Kt/V of 1.1.In the nocturnal arm there will be a minimum prescription of six hours per session for six days per week AND a minimum achieved standard Kt/V of 4.0. Patients will be followed for 12 months.

Because no previous randomized trials of nocturnal dialysis have been conducted, the first calendar year after the initiation of enrollment has been designated as a "Vanguard" phase during which feasibility of randomization and conduct of the interventions will be evaluated. If pre-defined benchmarks for establishment of feasibility are achieved during the Vanguard phase, the trial will proceed to its primary objective of determining if 6 times per week nocturnal hemodialysis results in clinically significant improvements in physiological, health-related quality of life (HRQL) and functional outcomes, as compared with three times per week conventional home hemodialysis.

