### 9.5 General Analytic Strategy for Quantitative Outcomes

The following analytic strategy will be employed for quantitative outcomes, including each of the main secondary outcomes with the exception of the rate of non-access hospitalization or death. The main analysis for each outcome will evaluate the treatment effect on the change from baseline to 12 months. For outcomes evaluated monthly (serum albumin and pre-dialysis phosphorus) the 12 month value will be averaged over the Months 10, 11, and 12 assessments for increased statistical power. For each outcome with multiple follow-up assessments (including the PHC, serum albumin, Beck Depression Inventory, Trailmaking Test B, and pre-dialysis phosphorus), an additional analysis will be conducted to evaluate the change from baseline to Month 4, where the Month 4 value is taken as the average value over months 3, 4, and 5 for serum albumin and pre-dialysis phosphorus. The analysis of change to 4 months will evaluate short term effects, while the analysis of change to 12 months will evaluate longer-term effects. The 4-month comparison is also intended to evaluate treatment effects prior to significant attrition. The "basic model" to be used for quantitative outcomes is:

$$\Delta \mathbf{Y}_{t} = \beta_{0t} + \beta_{1t} \operatorname{Trt} + \beta_{2t} \mathbf{Y}_{0} + \Sigma \gamma_{it} \mathbf{S}_{i} + \Sigma \delta_{it} \mathbf{F}_{i} + \varepsilon_{t}, \quad (\text{Basic Model})$$

where  $\Delta Y_t$  denotes the change in the response variable from baseline to time t, Trt is an indicator variable for the daily treatment intervention,  $Y_0$  is the baseline value of the response variable, the  $S_i$  are indicator variables for the Clinical Centers, the  $F_i$  are the following six pre-specified baseline covariates (age, race, years of dialysis, diabetic status, baseline serum albumin, and

FHN Nocturnal Protocol Version 3.3: October 15, 2008

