# 9.11 Statistical Power

Estimates of parameters for determination of study power were obtained primarily based on information from the HEMO Study database, with downward adjustments in mortality and hospitalization rates to account for the expectation of lower comorbidity among patients eligible for nocturnal dialysis. During the first year of follow-up in the HEMO Study, the mortality rate was 12%/year, the transplant rate was 4%/year, the rate of all non-access hospitalizations was 1.19 per year, and approximately 80% of patients remained in active follow-up at the 12 month assessment. To assure the power calculations are conservative, we have projected that mortality and hospitalization rates will be 40% lower in the control group of this trial than in the HEMO Study, and that transplantation rates will be slightly higher (6% per year instead of 4%), reflecting the expectation of a younger average age and inclusion of more incident patients. Data from the HEMO Study was also used to estimate the standard deviation of the change in the PHC, average serum albumin, average serum phosphorus, average pre-dialysis systolic blood pressure after controlling for the baseline value of outcome and pre-specified covariates. The standard deviation estimate of 24 g for the change in LV mass was estimated from the standard deviation of the change in LV mass by MRI obtained in 153 patients over 9 months by Pitt et al (2003).

The minimum detectable effect sizes for the co-primary PHC/Mortality and LV mass/Mortality composite endpoints of were estimated under the following assumptions: a) the target sample size of 90 randomized patients is achieved, b) exponentially distributed survival, with a 7%/yr mortality rate in the control group, c) exponentially distributed transplantation, with a 6%/yr transplantation rate in both treatment groups, d) measurements at 12 months of the PHC and LV mass outcomes will be obtained in 80% of randomized patients, e) normally distributed changes in the PHC and LV mass in those patients with 12-month measurements, with standard deviations (without covariate adjustment) of 9.12 PHC units and 24.0 g, respectively, f) utilization of the log rank test as described in Section 9.3, without covariate adjustment, and g) use of Hochberg's procedure to maintain an overall Type I error rate of  $\leq 5\%$ .

FHN Nocturnal Protocol Version 3.3: October 15, 2008

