Estimated Detectable Effect Sizes for 80% or 90% Power for the Primary Outcomes

 As described in the text, under the Hochberg procedure the statistical power for each of the two primary outcomes depends in part on the effect size for the other outcome. Thus, the minimum detectable effect on the LV mass-Mortality composite is evaluated assuming treatment effects on the change in the PHC of either 0, 2.28 (corresponding to 25% of the estimated standard deviation of the change in the PHC score after covariate adjustment), or 4.56 units (corresponding to 50% of one standard deviation). Similarly, the treatment effects on the PHC-Mortality composite are evaluated assuming effects of either 0, 6 (25% of 1 SD) or 12 g on the

change in LV mass. The simulation results indicate the above calculations are accurate if the correlation between the change in LV mass and the change in the PHC score is between 0 and +0.5.

Table 15 provides the estimated minimum detectable effect sizes for each of the quantitative main secondary outcomes under the following assumptions: a) measurements obtained at 12 months in 80% of patients for each outcome, b) the standard deviations of the changes in each outcome (with covariate adjustment) are as indicated in Table 15, c) two-sided significance levels of 0.05 are applied to each outcome, without adjustment for multiple tests, d) utilization of the parametric analysis of changes with covariate adjustment outlined in Section 9.5. The power calculations do not take into account information provided by the 4 month measurements for patients with missing data at 12 months; thus, in this respect the values are slightly conservative. As in Table 14, the minimum detectable effects are provided both overall (without parentheses), and among the assumed 95% of patients who complete the post-randomization component of the nocturnal training program (with parentheses), assuming no treatment effect among those not successfully completing the training program.

#### Table 15

Estimated Detectable Effect Sizes for 80% or 90% Power for the Main Secondary Outcomes

Outcome Variable	Assumed SD of 1 Yr Change	80% power	90% power
PHC (points)	8.310	5.54 (5.83)	6.40 (6.74)
LV mass (g)	24.00	16.0 (16.8)	18.5 (19.5)
Average Albumin (g/dL)	0.296	0.198 (0. 208)	0.229 (0.241)
Average serum phosphorus (mg/dL)	1.636	1.08 (1.14)	1.26 (1.33)
Beck Depression Inventory (1 SD) 	-	0.67 (0.71)	0.77 (0.81)

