Trailmaking Test B (1 SD) 	-	0.67 (0.71)	0.77 (0.81)

 Treatment effect tested at alpha = 0.05 using a 2-sided test.

 Detectable treatment effects expressed per 1 standard deviation of the changes in the Beck Depression Inventory and Trailmaking Test B because pilot data on 1-year changes in these

outcomes in dialysis patients is not available.

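### Section 9.8 sets the Watson volume and dialysis vintage interactions as two-group splits, which costs already weak tests about a third or more of their information if the modifier is roughly normal and acts linearly

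*Protocol*

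**What the plan says.** Protocol section 9.8 introduces a list of five effect modifiers: "The Steering Committee has pre-specified the following factors for evaluation of treatment interactions". Three are naturally two-group factors or are defined that way: history of heart disease, gender, and residual renal function by a urine volume threshold. The other two are continuous measurements given with a cut: "anthropometric volume (Watson volume < 35 L vs" 35 L or more, and "years of dialysis (< 2 years vs" 2 years or more. The protocol gives no reason for either cut, no expected share of patients on each side, no continuous version and no power for any interaction.

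Section 9.5 names years of dialysis among the "pre-specified baseline covariates (age, race, years of dialysis, diabetic status" and others, and does not say how it is coded. Archive notes in sections 2.7 and 9.9 record that prognostic covariates were later dropped from the analyses.

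**The concern.** The interaction analyses are meant to show whether some patients gain more or less from nocturnal dialysis. A split at 35 L treats patients at 34 L and 36 L as different kinds of patient and patients at 36 L and 55 L as the same. If benefit rises or falls smoothly with body water volume or vintage, part of that gradient lies within each group and the two-group test cannot use it. In a trial of 90 patients, interaction tests have no information to spare, so a real gradient becomes easier to miss. What is at stake is the reading of these additional analyses only.

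**Working it through.** **Inputs from the protocol.** Section 9.11 assumes that "the target sample size of 90 randomized patients is achieved" and, for the main secondary outcomes, "measurements obtained at 12 months in 80% of patients for each outcome". That gives 0.80 × 90 = 72 measured patients. Section 2.2 enrols "with equal allocation in each arm", so 36 per arm. The Table 15 footnote reads "Treatment effect tested at alpha = 0.05 using a 2-sided test". Table 15 gives an SD of 8.310 points for PHC and 24.00 g for LV mass. Section 5.1.2 hypothesises a 15 g effect on LV mass and cites 3 to 5 points as the important change on the SF-36 summary scores.

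**Not in the protocol.** The distributions of Watson volume and vintage, and the split at each cut. They are assumed below and shown as a range.

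**1. Reproduce Table 15 at 80% power.** Detectable effect = (1.960 + 0.842) × SD × √(2/36).
- PHC: 2.802 × 8.310 × 0.2357 = 5.49 points (5.56 with the t distribution); Table 15 has 5.54.
- LV mass: 2.802 × 24.00 × 0.2357 = 15.8 g (16.07 with t); Table 15 has 16.0.

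The table is reproduced.

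**2. Two-group interaction.** With share p above the cut, SE = SD × √[(4/72) × (1/p + 1/(1 − p))]. Detectable interaction at 80% power = 2.802 × SE. The last column is Φ(Table 15 effect/SE − 1.960).

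| Split | PHC (points) | LV mass (g) | Power for an interaction equal to the Table 15 effect |
|---|---|---|---|
| 50:50 | 11.0 | 31.7 | 29% |
| 70:30 | 12.0 | 34.6 | 25% |
| 80:20 | 13.7 | 39.6 | 20% |

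At an even split the detectable interaction is twice the detectable main effect. Power is 26% for a 15 g LV mass interaction, and 12% to 25% for 3 to 5 PHC points.

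**3. Information kept by the cut.** For a linear interaction this is the squared correlation between the modifier and its two-group indicator. For a normal modifier cut at quantile q it is φ(z_q)²/[q(1 − q)]:
- q = 0.5: 0.3989²/0.25 = 0.637, so 36% lost
- q = 0.3: 0.576, so 42% lost
- q = 0.2: 0.490, so 51% lost

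At a median cut, 72 patients act like 72 × 0.637 ≈ 46; at 80:20, like 72 × 0.490 ≈ 35.

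Other assumed shapes:
- Uniform, cut at the median: 25% lost.
- Watson volume as a two-sex mixture (means 42 to 45 L and 31 to 33 L, SD 4 to 6 L), cut at 35 L: 28% to 41% lost.
- Exponential vintage, cut at 2 years, mean vintage 1 to 6 years: 37% to 72% lost.
- True threshold exactly at the cut: nothing lost.

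**4. Effect on power, normal modifier, median cut.** For an interaction equal to the Table 15 effect, effect/SE is 5.54/(8.310 × 0.4714) = 1.414, and 16.0/(24.00 × 0.4714) gives the same. Split test: Φ(1.414 − 1.960) = 0.293. Continuous test: 1.414/√0.637 = 1.772, and Φ(1.772 − 1.960) = 0.426.

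For a larger interaction that gives 80% power on the continuous scale, the split gives Φ(2.802 × √0.637 − 1.960) = 0.61 at the median and 0.50 at 80:20. Simulated regression tests with 72 patients agree in direction and size: 76% falls to 54% at a median cut, and 75% to 49% at 70:30.

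**The case against.** Section 9.8 asks about subgroups, and fixed cuts answer that directly. They rule out cut points chosen after seeing the data, match the other three factors and need no linearity assumption. Two groups also work directly with the logrank analysis of the co-primary composites in section 9.3, which a term in the 9.5 model does not. All of this stands, and it is why the cuts should stay for display and for the composites.

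Vintage is also awkward as a continuous term. Section 2.5.2 reports that 20% to 30% of patients choosing nocturnal dialysis do so when dialysis starts, section 2.7 lets incident patients give baseline data after one week, and section 9.11 expects more incident patients than in the HEMO Study. A plain log creates extreme low values, and the raw scale gives long-vintage patients high leverage. Choosing the scale after seeing the data would add analyst freedom, so it must be fixed beforehand.

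A reader might go further in three ways that the protocol does not support:
- That at least a third of the information is always lost. This needs assumptions about shape and linearity, and the protocol gives no distribution.
- That section 9.5 enters years of dialysis continuously and so contradicts 9.8. It names the variable without stating its coding.
- That the diagnostics planned in 9.5 would cover linearity. They concern departures from normality, so a linearity check would have to be added.

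**Conclusion.** The point holds as a minor one. The protocol fixes both modifiers as two-group splits for the interaction tests. With a roughly normal modifier and a linear interaction, that loses about a third or more of the information: 36% at a median cut, rising to 51% at 80:20. The loss can be as low as 25% to 28% under the other smooth shapes tried, and is nil for a threshold at the cut.

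It would be wrong to infer that continuous terms make these tests adequate. For an interaction the size of the Table 15 effect, power rises from about 29% to about 43% in the ideal case and stays below one half. The fall from 80% to 61% applies only to an interaction much larger than the effects in Table 15. The gain is real, and it is confined to additional analyses.

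**What to change.** In section 9.8, for the quantitative outcomes analysed under 9.5, state that the treatment interactions with Watson volume and years of dialysis are tested with the modifier as a continuous term. Fix the scale in advance: litres for volume and, for vintage, for example log(years + a stated offset), because incident patients lie near zero. Add one pre-stated check for non-linearity. Keep the 35 L and 2-year groups for presenting estimates and for interaction analyses of the rank-based composites.

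Each test needs only the modifier's own term and its product with treatment, so dropping the prognostic covariates does not stand in the way. The cost is a few sentences and these model terms. The downside is a linearity assumption and some leverage from extreme values. Conduct, sample size, and the primary and main secondary analyses are unaffected.

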## 9.9 Missing Data

In spite of the relatively short follow-up of 12 months, a nontrivial loss-to-follow-up is inevitable in a study of HD due to high rates of death, transplant, and patient transfer to non-participating facilities. In the HEMO Study the combined loss-to-follow-up from death, transplant, and transfer was approximately 18% at 1 year.

Because all methods for accounting for missing data are subject to bias depending on untestable assumptions [Verbeke, 2000], efforts will be made to minimize missing data in the study design and conduct of the trials [Allison, 2001]. These include: 1) continuing data collection after safety stop-points or patient-termination of the treatment regimens, 2) provisions to obtain the key outcome results at a later time point should the patient be hospitalized at the target time for the visits, 3) monitoring and feedback regarding missing data throughout the trial, and 4) oral

administration of questionnaires.

Analytically, including prognostic baseline covariates and the early 4-month follow-up assessment should also reduce the chance of significant bias from missing data under the restricted maximum likelihood approach we propose. In this approach, bias from missing data at the 12-month assessment is reduced to the extent that relationships between the unobserved values of missing responses and the probability of missingness can be accounted for by either the baseline factors or the observed 4-month responses. [2014 FHN Archive Note: FHN Executive Committee dropped prognostic covariates from the analyses.] Nonetheless, some bias due to informative censoring [Little, 1995] is probably inevitable. Therefore, we plan to use a pattern mixture approach [Little, 1995] to perform sensitivity analyses of the estimated treatment effects under a range of assumptions regarding the association of the censoring times with the values of the missing responses [Daniels, 2000].

## 9.10 Analyses of Compliance

Rates of action items, stop points, dropouts, individual missed dialysis treatments and other aspects of compliance to the treatment regimens will be summarized by treatment group and related to baseline characteristics to ascertain what factors are associated with successful implementation of the treatment regimens. Reasons for dropouts and for noncompliance to the treatment interventions will also be tabulated by randomized group to assist in determining aspects of the interventions that may need to be altered in the design of a future hard endpoint full-scale trial.

# 9.11 Statistical Power

Estimates of parameters for determination of study power were obtained primarily based on information from the HEMO Study database, with downward adjustments in mortality and hospitalization rates to account for the expectation of lower comorbidity among patients eligible for nocturnal dialysis. During the first year of follow-up in the HEMO Study, the mortality rate was 12%/year, the transplant rate was 4%/year, the rate of all non-access hospitalizations was 1.19 per year, and approximately 80% of patients remained in active follow-up at the 12 month assessment. To assure the power calculations are conservative, we have projected that mortality and hospitalization rates will be 40% lower in the control group of this trial than in the HEMO Study, and that transplantation rates will be slightly higher (6% per year instead of 4%), reflecting the expectation of a younger average age and inclusion of more incident patients. Data from the HEMO Study was also used to estimate the standard deviation of the change in the PHC, average serum albumin, average serum phosphorus, average pre-dialysis systolic blood pressure after controlling for the baseline value of outcome and pre-specified covariates. The standard deviation estimate of 24 g for the change in LV mass was estimated from the standard deviation of the change in LV mass by MRI obtained in 153 patients over 9 months by Pitt et al (2003).

The minimum detectable effect sizes for the co-primary PHC/Mortality and LV mass/Mortality composite endpoints of were estimated under the following assumptions: a) the target sample size of 90 randomized patients is achieved, b) exponentially distributed survival, with a 7%/yr mortality rate in the control group, c) exponentially distributed transplantation, with a 6%/yr transplantation rate in both treatment groups, d) measurements at 12 months of the PHC and LV mass outcomes will be obtained in 80% of randomized patients, e) normally distributed changes in the PHC and LV mass in those patients with 12-month measurements, with standard deviations (without covariate adjustment) of 9.12 PHC units and 24.0 g, respectively, f) utilization of the log rank test as described in Section 9.3, without covariate adjustment, and g) use of Hochberg's procedure to maintain an overall Type I error rate of  $\leq 5\%$ .

FHN Nocturnal Protocol Version 3.3: October 15, 2008

The minimum detectable treatment effects under the above assumptions were estimated by statistical simulation, and are presented in Table 14. Two calculations of the minimum detectable effect are provided for each scenario. The first calculation (without parentheses), represents the minimum detectable overall treatment effect among all randomized patients, averaging over both the nocturnal group patients who successfully complete the training program and those who do not. The second calculation (in parentheses), represents the minimum detectable treatment effect among those who successfully complete the training program an implement the nocturnal therapy, assuming i) that 95% of patients randomized to the nocturnal arm successfully complete the final two weeks of the training program specific to nocturnal therapy, and ii) that the treatment effect is 0 among those who do not complete the training program. Under Hochberg's procedure the threshold used to test the significance of each of the two co-primary endpoints depends on the other; hence, as indicated in the table, the minimum detectable effect size for the PHC/Mortality composite depends in part on the magnitude of the treatment effect on LV mass, and the minimum detectable effect size for the LV mass/Mortality composite depends on the size of the treatment effect on the PHC. Under a hypothesized treatment effect leading to a 20% reduction in the mortality rate, the target sample size of 90 patients has 90% power to detect overall treatment effects ranging from 8.38 to 8.64 points for the change in SF-36 PHC score, depending on the size of the treatment effect on LV mass. Similarly, the study has 90% power to detect treatment effects ranging from 22.0 to 22.7 g for the change in LV mass, depending on the size of the treatment effect on the PHC. Under the stated assumptions, these overall minimum detectable effects translate to treatment effects ranging from 8.82 to 9.09 points for the PHC and from 23.2 to 23.9 g for LV mass among the 95% of randomized patients who successfully complete the training program.

#### Table 14

Outcome	Treatment Effect on Other Primary Outcome	80% power	90% power
LV mass - Mortality	0	19.8 (20.8) g	22.7 (23.9) g
	2.28 g	19.6 (20.6) g	22.6 (23.8) g
	4.56 g	19.0 (20.0) g	22.0 (23.2) g
PHC - Mortality	0 units	7.52 (7.92) units	8.64 (9.09) units
	6 units	7.44 (7.83) units	8.59 (9.04) units
	12 units	7.23 (7.61) units	8.38 (8.82) units

Estimated Detectable Effect Sizes for 80% or 90% Power for the Primary Outcomes

 As described in the text, under the Hochberg procedure the statistical power for each of the two primary outcomes depends in part on the effect size for the other outcome. Thus, the minimum detectable effect on the LV mass-Mortality composite is evaluated assuming treatment effects on the change in the PHC of either 0, 2.28 (corresponding to 25% of the estimated standard deviation of the change in the PHC score after covariate adjustment), or 4.56 units (corresponding to 50% of one standard deviation). Similarly, the treatment effects on the PHC-Mortality composite are evaluated assuming effects of either 0, 6 (25% of 1 SD) or 12 g on the

change in LV mass. The simulation results indicate the above calculations are accurate if the correlation between the change in LV mass and the change in the PHC score is between 0 and +0.5.

Table 15 provides the estimated minimum detectable effect sizes for each of the quantitative main secondary outcomes under the following assumptions: a) measurements obtained at 12 months in 80% of patients for each outcome, b) the standard deviations of the changes in each outcome (with covariate adjustment) are as indicated in Table 15, c) two-sided significance levels of 0.05 are applied to each outcome, without adjustment for multiple tests, d) utilization of the parametric analysis of changes with covariate adjustment outlined in Section 9.5. The power calculations do not take into account information provided by the 4 month measurements for patients with missing data at 12 months; thus, in this respect the values are slightly conservative. As in Table 14, the minimum detectable effects are provided both overall (without parentheses), and among the assumed 95% of patients who complete the post-randomization component of the nocturnal training program (with parentheses), assuming no treatment effect among those not successfully completing the training program.

#### Table 15

Estimated Detectable Effect Sizes for 80% or 90% Power for the Main Secondary Outcomes

Outcome Variable	Assumed SD of 1 Yr Change	80% power	90% power
PHC (points)	8.310	5.54 (5.83)	6.40 (6.74)
LV mass (g)	24.00	16.0 (16.8)	18.5 (19.5)
Average Albumin (g/dL)	0.296	0.198 (0. 208)	0.229 (0.241)
Average serum phosphorus (mg/dL)	1.636	1.08 (1.14)	1.26 (1.33)
Beck Depression Inventory (1 SD) 	-	0.67 (0.71)	0.77 (0.81)
Trailmaking Test B (1 SD) 	-	0.67 (0.71)	0.77 (0.81)

 Treatment effect tested at alpha = 0.05 using a 2-sided test.

 Detectable treatment effects expressed per 1 standard deviation of the changes in the Beck Depression Inventory and Trailmaking Test B because pilot data on 1-year changes in these

outcomes in dialysis patients is not available.

